11 STATISTICAL ANALYSIS METHODS

11.1 Descriptive Statistics

Descriptive statistics will be applied to describe patient characteristics (e.g. age, gender, aetiologies) and the examined study outcomes. For quantitative data the mean, the standard deviation (SD), and/or the median with range (minimum and maximum values) will be calculated. For qualitative data absolute and relative frequencies will be used.

The number (n) and the percentage (%) of AEs will be recorded according to causality as defined in the CIP.

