8.5 Early Withdrawal

8.5.1 Reason for Early Withdrawal

The Investigator may decide to withdraw a subject from the study for one of the following reasons upon agreement with MED-EL:

- Health issues (e.g. occurrence of SAEs, subject's death, etc.)
- Further participation would cause an unacceptable risk to the subject
- The subject moved away
- The subject does not comply with the CIP (e.g. s/he does not attend the visits on schedule; she/he does not communicate relevant medical issues to the Investigator, etc.)

In accordance with the Declaration of Helsinki (Fortaleza, 2013), subjects are free to terminate their participation in the study at any time for any or for no reason, without prejudicing their basic right to receive the best treatment available for them.

If a subject decides to withdraw early, he/she must return the SONNET 2 audio processor.

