8.5.2 Handling of Early Withdrawal

Withdrawal of any subjects shall be recorded by the Investigator in the appropriate CRF "Early Withdrawal". If a subject decides to withdraw from the study, every effort should be made to contact him/her and to obtain information about the reason(s) for discontinuation and/or any AEs experienced. Subjects withdrawing prematurely won't be followed-up actively unless they suffer from an ongoing AE. In the case of an ongoing AE, the procedure described in section 8.8 of this CIP shall be followed.

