10.2 Analysis Population

The Per Protocol Analysis (PP) will include all patients who adhere to the major criteria of the protocol; otherwise that patient will be excluded from the analysis.

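### The SAP defines only a per-protocol set and names no population or denominator for the adverse event summary, so subjects excluded from that set could be left out of it

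*SAP*

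**What the plan says.** **Population.** SAP 10.2 has one rule: "The Per Protocol Analysis (PP) will include all patients who adhere to the major criteria of the protocol". The consequence for anyone else is given without qualification: "otherwise that patient will be excluded from the analysis". The visible SAP defines no safety, full-analysis or all-enrolled set and does not list the major criteria.

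**AE summary.** SAP 11.1: "The number (n) and the percentage (%) of AEs will be recorded according to causality". The protocol is invoked for the definition of causality. No population is named, and it is not said whether the percentage is of subjects or of events.

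**Withdrawal.** Protocol 8.5.1 lists, as separate reasons, "Health issues (e.g. occurrence of SAEs, subject's death, etc" and "The subject does not comply with the CIP".

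**AE data at withdrawal.** Protocol 8.5.2 asks for every effort "to obtain information about the reason(s) for discontinuation and/or any AEs experienced". That sentence is worded for subjects who decide to leave. Protocol 8.8.1 adds up to eight weeks of follow-up for device- or procedure-related events and serious events that are ongoing when participation ends.

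**Protocol populations.** Protocol 4.6 names an actual population (everyone enrolled, whatever happens later) and an analytic population (those meeting unlisted analysis criteria). It equates the study population with the latter. In the available text the all-enrolled group is assigned to no analysis.

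**Sample size.** Protocol 7.3 and SAP 8 calculate a minimum of 13. They set a maximum of 30 to cover about 20% dropout and to gather further safety and efficacy data.

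**The concern.** A safety summary normally counts everyone exposed to the device, because subjects who leave or break the rules may do so for reasons linked to harm. Here the only stated population rule is one of adherence, and the AE sentence offers no alternative. An analyst following the SAP in order has one defined set to use for that table.

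At stake is whether the AE summary is complete. The SAP states in section 3 that it exists to prevent post hoc decisions. However, the study is open label, the major criteria are undefined, and SAP 13 leaves deviations that could affect the analysis to discussion among sponsor roles. Who is counted for safety would be settled late, possibly with the events already known.

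**Working it through.** **1. The plan's own figure.** The documents give no AE count, rate or denominator, so there is none to reproduce. The one related figure is the minimum of 13, which shows how much of the enrolment cap rests on the wish for more data.

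- Inputs: margin 2 dB, one-sided alpha 0.025, power 90%, SDs 1.586 and 1.463 (protocol 7.3, SAP 8).
- Assumptions, because the plan does not state them: σ is the root mean square of the two SDs, √[(1.586² + 1.463²)/2] = 1.526; the true difference is 0; r = 1.
- N = (1 + 1/1) × [1.526 × (1.960 + 1.282)/(0 − 2)]² = 12.2, rounded up to 13. The figure reproduces.
- Allowing for 20% dropout: 13/0.80 = 16.25, rounded up to 17. So up to 30 − 17 = 13 of the 30 places rest on the aim of gathering more safety and efficacy data.

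**2. Who would leave the AE table if 10.2 governs it.**

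- *Non-compliance with the protocol.* The test in 10.2 is adherence, so this is the direct route. Even so, not every lapse need breach a major criterion.
- *Withdrawal for a serious event.* Protocol 8.5.1 lists this apart from non-compliance. Such a subject leaves the per-protocol set only if completing the study is one of the unlisted major criteria.

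**3. Possible effect on the percentage of subjects with an AE.** All counts are assumed: 30 subjects receive the device and 1 to 6 are excluded. The upper end, 6, is 20% of 30; it borrows the dropout allowance, which is not the same thing as per-protocol exclusion.

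| Excluded | AE among excluded | AE among kept | Per protocol | All 30 | Per protocol minus all |
|---|---|---|---|---|---|
| 1 | 1 | 0 | 0/29 = 0.0% | 1/30 = 3.3% | −3.3 points |
| 6 | 6 | 0 | 0/24 = 0.0% | 6/30 = 20.0% | −20.0 points |
| 1 | 1 | 3 | 3/29 = 10.3% | 4/30 = 13.3% | −3.0 points |
| 6 | 6 | 3 | 3/24 = 12.5% | 9/30 = 30.0% | −17.5 points |
| 1 | 0 | 3 | 3/29 = 10.3% | 3/30 = 10.0% | +0.3 points |
| 6 | 0 | 3 | 3/24 = 12.5% | 3/30 = 10.0% | +2.5 points |

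The first four rows are extreme, because every excluded subject has an AE. In the last two rows no excluded subject has one: the count is unchanged, only the denominator shrinks, and the per-protocol percentage is slightly too high. The sign therefore depends on who is excluded.

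**4. If the percentage is of events.** The wording of 11.1 can equally mean the share of all AEs in each causality category. The table above then does not apply. Excluded subjects' events would still drop out of both the category counts and the total, so the population question remains.

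**The case against.** The strongest reply is that the SAP never places the AE summary on the per-protocol set. SAP 11.1 names no population. The exclusion in 10.2 can be read as applying only to the per-protocol analysis itself, just as SAP 7.6.4 uses exclusion for single questionnaires. The AE section of the protocol (section 12, cited in protocol 18.1) and SAP section 16 are not in the public text and may say more. Protocol 8.5.2 and 8.8.1 show an intention to capture events from subjects who leave. Finally, this is a post-market study of a CE-marked device with no safety objective or endpoint, and AEs are only described.

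Much of this stands. A reader might infer that the SAP definitely leaves out the subjects withdrawn for serious events and so under-reports harm selectively. The documents do not support that: the exclusion is one reading of 10.2, withdrawal for a serious event is not itself non-adherence, and no AE rate is available to show a direction. Nor can it be said that the unavailable sections are silent.

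What does not stand is the conclusion that nothing needs changing. Protocol 15.6 refers the detailed analysis to the SAP, and both the SAP's population rule and its AE sentence are visible. If protocol section 12 does count everyone, SAP 10.2 and 11.1 still need to be brought into line with it. Collecting events from withdrawn subjects does not settle whether they are tabulated.

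**Conclusion.** The point holds as a gap in specification with a foreseeable consequence. The visible SAP has a per-protocol set only, with undefined criteria and no safety exception, and it gives the AE summary neither a population nor a denominator. Followed literally, subjects outside the per-protocol set would be missing from that summary, although their AE information is sought and further safety data are part of the reason for enrolling up to 30.

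Neither the size nor the direction of the effect can be computed from the documents. The range shown, from 20.0 points too low to 2.5 points too high, rests on assumed counts, on percentages being of subjects, and on AEs being tabulated on the per-protocol set. The primary non-inferiority comparison is not affected by this point.

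**What to change.** - Add to SAP 10.2 a safety set: all enrolled subjects who received a SONNET 2, including those withdrawn early.
- State in SAP 11.1 that every AE count and percentage is based on this set.
- State in 11.1 whether the percentage is of subjects or of events. If both are wanted, give both with their denominators.
- Check the wording against the AE section of the protocol so that the two documents agree.

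Cost: a few sentences in the SAP, to be in force before the final analysis. It requires no additional data collection, visits or subjects. This is a free improvement.

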11.2 Inferential Statistics

11.2.1 Primary Objectives

The mean difference (dB SNR) with the 95% confidence intervals of the OLSA in noise speech test (S0N0) between the SONNET and the SONNET2 will be calculated to examine if the mean difference lies below the a-priory specified non-inferiority margin of 2 dB.

11.2.2 Secondary Objectives

The secondary objectives of this study are of an explorative nature and provide additional evidence on the performance of SONNET 2-specific front-end features. The performance of the SONNET 2 will be assessed with different combinations of frontend processing features under different environmental test conditions using the following tests:

- Speech performance
 - ◆ Freiburg Monosyllabic test in quiet; speech presented from the front
 - ◆ Oldenburg Sentence Test in noise in the set-ups:
 - ⇒ S0N0
 - ⇒ S0N0T0
 - ⇒ S0, ±N45, ± N135
- Quality of hearing in real life
 - ◆ HISQUI19
 - ◆ SSQ12
- Device handling

- ◆ Data Logging
- ◆ APSQ
- Subjective Rating
 - ◆ ACALES
 - ◆ Subjective Sound Quality Rating
 - ◆ Product Specific Questionnaire

The Kolmogorov-Smirnov test, the Shapiro-Wilk test and a graphical examination will be conducted in a first step to check the data distribution of the secondary endpoints. Based on the data parametric and/or non-parametric tests such as the Paired sample t-test or the Wilcoxon signed-rank test will be applied.

12 Data Handling

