9.2 Follow-up Visit 1 (2nd study visit)

The first follow-up visit will be scheduled 2 weeks (± 1 week) after the first study visit.

During this visit, fittings of the SONNET and the SONNET 2 or will be confirmed prior to any study test and only adjusted if needed.

9.2.1 Testing with the current audio processor (SONNET):

- Speech test in noise (S0N0)

9.2.2 Testing with the SONNET 2:

- User satisfaction and sound quality rating via questionnaires
- MAESTRO Export of all SONNET 2 configurations including the data logging information
- Speech test in noise (S0N0)
 - ❖ Set-up as an OPUS 2
 - ❖ Set-up as an SONNET (without new front-end features)
 - ❖ Setting 1: ASC off, mild WNR, mild NR, mild TR
 - ❖ Setting 2: ASC off, mild WNR, strong NR, strong TR
 - ❖ Setting 3: ASC mild, mild WNR, auto NR, auto TR
 - ❖ Setting 4: ASC strong, strong WNR, auto NR, auto TR
- Speech test in noise (S0N0T0)
 - ❖ Set-up as an SONNET (without new front-end features)
 - ❖ Setting 1: ASC off, mild WNR, mild NR, mild TR
 - ❖ Setting 2: ASC off, mild WNR, strong NR, strong TR
- Reset the data logging in all configurations
- Send subject home with two SONNET 2 configurations (randomized across subjects) with data logging set to zero

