4.2 Purpose of the Analyses

This study will investigate the impact of ASM 3.0 as implemented in the SONNET 2 on CI users' speech performance and their subjective quality of hearing.

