5 STUDY OBJECTIVES

5.1 Primary Objective

- Comparison between the speech reception thresholds in the OLSA test in noise (S0N0) of the SONNET 2 programmed as a SONNET and the SONNET 2 (setting 1; ASC off, mild WNR, mild NR, mild TR).

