8 SAMPLE SIZE

The primary objective of this study is to show non-inferiority of SONNET2 in a OLSA in noise speech test (S0N0) compared to the SONNET. The margin of non-inferiority is set to 2 dB SNR.

Comparable data of the final report "Performance of Cochlear Implant Patients with Microphone Directionality and Wind Noise Reduction with the "SONNET" of the OLSA in noise speech test (S0N0) were used as basis for the sample size calculation:

OPUS2	mean: 0.589 dB;	± SD: 1.586 dB vs.
SONNET natural-MILD	mean: -0.088 dB;	± SD: 1.463 dB

The sample size was estimated using the formula on noninferiority (Chow, Shao et al. 2008):

$$N = (1 + \frac{1}{r})(\sigma \frac{Z_{crit} + Z_{pwr}}{(\mu_A - \mu_B) - \Delta})^2$$

Assuming a non-inferiority margin of 2 dB (Δ), with an alpha-level of 0.025 (noninferiority, one-sided) and a power of 90%, a minimum sample size of 13 subjects was calculated (Z_{crit} is the normal quantile for the 0.025 alpha level, and Z_{pwr} is the normal quantile for the 90% power). To allow for possible dropouts (approximately 20%) and to provide additional safety and efficacy data, a maximum of 30 subjects will be included in this study.

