9 HYPOTHESES

9.1 Hypothesis for the Primary Objective

The primary objective of this study is to show non-inferiority of SONNET2 in a OLSA in noise speech test (S0N0) compared to the SONNET. The margin of non-inferiority is set to 2 dB SNR.

- Verbal formulation

Hypothesis H₀ (Null Hypothesis):

Speech perception with the SONNET 2 in its default setting in the OLSA in noise (S0N0) is inferior to the speech perception in the same test condition with the SONNET. A mean difference of ≥ 2 dB is considered as a clinically relevant difference.

Hypothesis H₁ (Alternative Hypothesis):

Speech perception with the SONNET 2 in its default setting in the OLSA in noise (S0N0) is non-inferior to the speech perception in the same test condition with the SONNET. A mean difference of less than 2 dB is not considered as a clinically relevant difference.

- Mathematical formulation

$$H_0: \mu_1 - \mu_2 \geq \Delta \text{ (2 dB SNR)}$$

$$H_1: \mu_1 - \mu_2 < \Delta \text{ (2 dB SNR)}$$

Where: μ_1 = mean OLSA in noise (S0N0) results as dB SNR with the SONNET

μ_2 = mean OLSA in noise (S0N0) results as dB SNR with the SONNET2

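### For settings 2 to 4, including the only two with the scene classifier on, the SAP names only tests of zero difference on S0N0; three paired confidence intervals shown next to 2 dB would say what loss the data exclude

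*SAP*

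**What the plan says.** SAP 4.2 gives the purpose: "This study will investigate the impact of ASM 3.0 as implemented in the SONNET 2". SAP 4.1 lists what ASM 3.0 adds: noise reduction (NR), transient reduction (TR) and an automatic scene classifier (ASC).

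The primary objective (SAP 5.1, Protocol 5.1) compares the SONNET 2 programmed as a SONNET with "SONNET 2 (setting 1; ASC off, mild WNR, mild NR, mild TR". SAP 11.2.1 reads the SONNET versus SONNET 2 difference as a mean with a 95% confidence interval against 2 dB. SAP 9.1 adds: "A mean difference of less than 2 dB is not considered as a clinically relevant difference".

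Protocol Table 2 and section 9.2.2 define three further new settings. Setting 2 has the classifier off and strong NR and TR. Setting 3 has the classifier on mild. The last is "Setting 4: ASC strong, strong WNR, auto NR, auto TR". All six SONNET 2 configurations are tested on S0N0 at Visit 2.

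For everything outside the primary comparison, SAP 11.2.2 says: "Based on the data parametric and/or non-parametric tests such as the Paired sample t-test or the Wilcoxon signed-rank test will be applied". Protocol 15.1.2.1 likewise plans to look for a statistically significant difference. SAP 12.1.1 applies Holm-Bonferroni to multiple comparisons without naming the family. SAP 9.2 calls the secondary analyses exploratory and states no hypotheses for them.

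**The concern.** One of the three features that make up ASM 3.0, the scene classifier, is switched off in the only comparison that is read against a margin. Strong NR and TR, fixed in setting 2, are not in it either. For the settings that do carry these features, the named tests ask whether the mean difference is zero. The plan's own yardstick for S0N0 asks something else: is the loss smaller than 2 dB?

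A p-value against zero answers that question in neither direction. A non-significant result does not bound the loss, and a significant one may reflect a loss that the SAP regards as not clinically relevant. Holm adjustment protects against false differences, but it also makes a real loss more likely to go undetected. At stake is how much the study can say about three of its four new settings from data it collects anyway.

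**Working it through.** **Inputs from the documents (SAP 8, Protocol 7.3).** Planning SDs 1.586 and 1.463 dB; "The margin of non-inferiority is set to 2 dB SNR"; one-sided alpha 0.025; power 90%; "a minimum sample size of 13 subjects was calculated"; maximum 30 subjects, about 20% dropout, so 30 × 0.8 = 24 completers.

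**Assumption.** The within-subject correlation ρ is not given. I show 0, 0.5 and 0.8.

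**1. The plan's own figure.** Pooled SD = √[(1.586² + 1.463²)/2] = 1.526 dB. With a true difference of 0, the SAP formula with equal allocation gives 2 × [1.526 × (1.960 + 1.282)/2]² = 12.2, rounded up to 13. The stated minimum reproduces. The formula is the two-sample form; the steps below use paired differences.

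**2. SD of the paired difference.** SD_d = √(1.586² + 1.463² − 2ρ × 1.586 × 1.463) = 2.16 / 1.53 / 0.97 dB for ρ = 0 / 0.5 / 0.8.

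**3. Half-width of the 95% interval,** t(0.975, n−1) × SD_d/√n:

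| n | ρ = 0 | ρ = 0.5 | ρ = 0.8 |
|---|---|---|---|
| 13 | 1.30 dB | 0.92 dB | 0.59 dB |
| 24 | 0.91 dB | 0.65 dB | 0.41 dB |

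**4. Chance that a true 2 dB loss is non-significant** (two-sided paired t-test, noncentral t with noncentrality 2√n/SD_d):

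| n | Level | ρ = 0 | ρ = 0.5 |
|---|---|---|---|
| 13 | 0.05 | 13% | 1% |
| 13 | 0.05/3 | 29% | 4% |
| 24 | 0.05 | 0.9% | <0.01% |
| 24 | 0.05/3 | 3% | 0.02% |

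At ρ = 0.8 every entry is below 0.01%. The 0.05/3 rows are the first Holm step over settings 2, 3 and 4. If the family were all 21 pairs of the seven tested conditions, the first step at n = 13 would give 62% / 22% for ρ = 0 / 0.5, and at n = 24 15% / 0.3%.

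**5. The other direction.** A true 1 dB loss lies inside the margin. At n = 24 the unadjusted test is significant in 59% / 87% of trials (ρ = 0 / 0.5).

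**6. What a non-significant result leaves open.** Take the observed SD as planned. At the first Holm step over three comparisons, a result just short of significance has an upper 95% limit of (t at 0.05/3 + t at 0.05) × SD_d/√n:
- n = 13, ρ = 0.5: (2.78 + 2.18) × 1.53/√13 = 2.10 dB
- n = 24, ρ = 0: (2.58 + 2.07) × 2.16/√24 = 2.05 dB
- n = 24, ρ = 0.5: (2.58 + 2.07) × 1.53/√24 = 1.45 dB

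So the same verdict of not significant can go with a 2 dB loss excluded or not excluded. The interval shows which; the p-value does not.

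**7. What the interval offers.** If a setting is truly 2 dB worse, its upper 95% limit falls below 2 dB in 2.5% of trials, per comparison. If it is truly equal, the limit falls below 2 dB in 87% / 99% of trials at n = 13 (ρ = 0 / 0.5), and in 99% or more at n = 24. At one-sided 0.025/3, the first Holm step over three settings, the figures are 71% / 96% at n = 13 and 97% or more at n = 24.

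**The case against.** The strongest reply is that the secondary analyses are openly exploratory. SAP 9.2 states no hypotheses and says they do not affect the primary result. The secondary objective is a comparison across settings, not non-inferiority of each one, and the features are meant to improve performance in specific environments, so a two-sided difference test is a reasonable tool. Limiting the confirmatory claim to setting 1 is a legitimate choice of scope. All of this stands, and it is why the point is an improvement rather than a defect.

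The named tests are also not exhaustive: SAP 11.2.2 introduces them with 'such as', SAP 11.1 provides means and SDs for every outcome, and SAP 12.1 sets a general 95% confidence level. That leaves room for intervals, but no section ties an interval or the margin to settings 2 to 4, and SAP 3 says the plan exists to avoid post hoc decisions.

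A reader might infer that the sponsor will report a non-significant result as preserved speech perception. Neither document says so. A reader might also take 62% as the typical chance of missing a 2 dB loss. That figure needs three things together: 13 subjects, zero correlation in a design where each subject is their own control, and a 21-pair Holm family that the SAP does not define.

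Finally, calling three settings non-inferior at 2.5% error each would leave the error across settings uncontrolled (up to 3 × 2.5% = 7.5%). That objection is right, and the fix below allows for it.

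**Conclusion.** The point holds as a low-cost improvement to SAP 11.2.2. The primary analysis is not affected, and the documents do not contradict themselves on this point. For settings 2 to 4 the named tests do not show how large a loss on S0N0 the data exclude, although the data and a 2 dB limit are both available.

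The practical risk of missing a full 2 dB loss is modest. It is concentrated near 13 subjects, after Holm adjustment and at low correlation; with 24 completers it is at most about 3% for a three-comparison family. The stronger case for intervals is that they make the result readable against the plan's own criterion, whichever way the p-value falls.

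These figures rest on the planning SDs, which come from a comparison of OPUS 2 with SONNET in an earlier study, on normally distributed paired differences, and on correlations that the documents do not give. The margin is stated for S0N0 only, so the conclusion does not extend to the five-loudspeaker set-up.

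**What to change.** Reconcile two things before the margin is used. Protocol 10.2.3 defines the threshold as SRT50, SAP 7.6.2 as SRT80. H1 in Protocol 6.1 and SAP 9.1 is written as SONNET minus SONNET 2 below 2 dB, whereas with a lower threshold being better, a loss with SONNET 2 appears as SONNET 2 minus SONNET.

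Then add to SAP 11.2.2:

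> For S0N0 at Visit 2, the mean paired difference (setting minus SONNET 2 programmed as SONNET) with its two-sided 95% confidence interval will be reported for settings 2, 3 and 4 and shown next to the 2 dB margin. These intervals are exploratory and have no effect on the primary conclusion. A non-significant p-value will not be reported as preserved speech perception. Any statement that one of these settings is non-inferior requires Holm adjustment over the three comparisons.

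The cost is three intervals from data already planned and a few lines of text, with no extra subjects or tests. The downside is that there are three more exploratory results to report, and that a setting whose interval reaches 2 dB must be described as not shown.
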